6.1.3. Management of women who drop out prior to receiving MUS

It is possible that some women in both groups may cancel their surgical MUS procedure due to personal reasons, or other. It is also possible that women randomized to BPTx may cancel their surgical procedure if they receive preoperative BPTx treatment and experience improvement. These women will still be included from an ITT perspective.

6.2. Statistical analysis plan

6.2.1. Primary aim

The mean change from baseline in UDI scores will be compared between groups at 1 year. As explained previously, participants will be permitted to seek additional treatment for SUI and/or OAB after 3 months following MUS. Because such treatment is expected to impact the participant’s UDI score at 1 year, we will use an analysis method that accounts for the impact of additional treatment. Specifically, a general linear mixed model will be constructed to model change from baseline in UDI scores using scores recorded

at time points up to 1 year following MUS. For participants who request additional treatment, only UDI measurements up to the time of additional treatment will be included in the model, and measurements taken between additional treatment and 1 year will be considered missing for the purpose of the primary analysis. The model will include fixed effects for treatment group, time, request for additional treatment, and interactions between those variables. It will also be adjusted for the design effects of stratification by center and by baseline urge IE group. Thus, the models will allow for different trajectories of change for women who are or are not randomized to BPTx and for those who do or do not request additional treatment. A statistical test based on the model will be conducted to assess whether mean changes from baseline in UDI scores at 1 year are significantly different between the two treatment groups, accounting for the percent of women in each group who request additional treatment. Sensitivity analysis will be conducted to test the robustness of test results to model specifications.

We will report whether change in total UDI score between baseline and one year is significantly different in the two groups. If the difference is statistically significant, the potential clinical significance of the difference will be discussed. We recognize that our sample size would allow us to find a difference between groups that is statistically significant yet smaller than published MIDs for total UDI score for women with MUI. However, published MIDs were calculated based on populations that may be somewhat different from the one targeted for enrollment in ESTEEM, and a secondary aim of ESTEEM is to explore whether the true MID in this population differs from previously published values.

6.2.2. Secondary aims

The mean change from baseline in UDI-irritative and UDI-stress scores at 1 year will be compared between groups using the same analysis methods described for the primary outcome. If the difference is statistically significant, the potential clinical significance of the difference will be discussed. Additional analyses will be conducted to determine whether the MIDs in this MUI population differ from previously published MIDs.

6.2.3. Exploratory aims

a. Other UUI/OAB outcomes

Bladder diary

We will compare change in number of urge IEs and urgency-episodes and nocturia episodes between groups from baseline to 6 and 12 months. Of note, not all four symptoms of OAB (frequency, urgency, nocturia, and UUI) are required to be present at baseline for eligibility into this trial (only UUI required). Changes from baseline in bladder diary outcomes will be calculated and analyzed using the methods described for the analysis of the primary outcome.

For urinary frequency, women reporting on average >8 voids/24 hours at baseline will be considered symptomatic, and normalization of voiding frequency will be defined as ≤ 8 voids/24 hours at 1 year. A 50% improvement will be defined as a reduction by half in the number of voids that patients had at baseline. The number of women who had normalization of voiding frequency and 50% improvement will be compared between groups separately and collectively. We will also assess the proportion of women who had worsening of urinary frequency (includes women who developed de novo frequency and those who worsened). These dichotomous outcomes will be analyzed using logistic regression, controlling for the design effects of stratification by center and by baseline urge IE group. To assess the impact of additional treatment prior to 1 year, sensitivity analyses will be conducted in which women who request additional treatment will be assigned the less-favorable outcome.

OAB-SAT-q and OAB-q

For these scales and associated subscales, differences from baseline will be calculated for the OAB-q, and methods described for analysis of the primary outcome will be used to test for differences between treatment groups at 12 months. For the OAB-SAT-q, differences in post-treatment scores will be compared between groups.

b. Differences in time to failure between groups

Although our primary outcome is at 12 months, the team was interested in whether perioperative BPTx may be associated with a delayed *time to failure* compared to Control. In other words, is BPTx associated with a significant effect, but the effect is not sustained at the 12 month time point? For example, if BPTx could delay the need for anti-muscarinics for up to 9 months, this would be relevant information for counseling women and perhaps clinically recommending perioperative BPTx. As described previously, failure will be defined as initiation of any additional treatment for either SUI or UUI/OAB symptoms.

A class of survival model which can account for interval censoring (outcomes measured at pre-planned time points as opposed to continuously over time) will be used to determine if combined MUS+BPTx is associated with a decrease time to failure compared to MUS alone between 3-12 months. Depending on the distribution of the observed data, an accelerated failure time frailty model or a Bayesian survival model may be used. The model will be adjusted for the design effects of stratification by center and by baseline urge IE group.

c. Predictors of treatment success and failure

Regression models will be created to identify predictors of change from baseline to 1 year for UDI total score and stress and irritative subscale scores. Participants who request additional treatment prior to 1 year will not be included in the predictive models. Potential predictors will include age, diary parameters such as number of UUI episodes/3 days, functional bladder capacity, bother severity at baseline. The relationship between potential predictors and outcomes will be explored in models that include one predictor plus stratification factors (center and baseline urge IE group). Predictive models will be constructed using backward selection of predictors. The impact of collinearity between predictors will be assessed and the final model modified as necessary.

d. Quality of life/global impression

For these scales and associated subscales, differences from baseline will be calculated and methods described for analysis of the primary outcome will be used to test for differences between treatment groups from baseline and 6 and 12 months.

e. To describe safety and initiation of additional treatment for worsening OAB and/or persistent SUI

We will describe rates of sling revision due to worsening OAB symptoms and rates of additional treatment.

f. To determine MIDs and clinically meaningful MUI definitions that predict clinical outcomes.

We will explore potential MIDs for UDI total score and stress and irritative subscores for this MUI population. MIDs will be calculated using anchor- and distribution-based approaches. Potential anchors include global impression of change, incontinence episodes from the bladder diary, and request for additional treatment.

We will attempt to create threshold definitions, based on baseline measures of the UDI, IIQ, OAB-q, UDE, and baseline bladder diary parameters in isolation and in combination, that are predictive of clinical success at 1 year. Definitions of success will be based on a change from baseline in total UDI score, UDI-irritative score or UDI-stress score at least as large as the MID for this MUI population.

g. To compare pelvic floor muscle strength changes between women randomized to combined MUS+BPTx versus MUS alone, to estimate associations between pelvic floor muscle strength improvement and UI symptoms, and to identify predictors of unsuccessful pelvic floor muscle strengthening and urge suppression and their effects on urinary outcomes in women randomized to BPTx

As mentioned above, all women will undergo PFM strength measurements using the Peritron device by masked coordinators at baseline, postoperative at 2 weeks, 8 weeks (end of intervention), and 12 months (primary endpoint). The difference in the maximum pelvic floor muscle contraction pressure (maximum amplitude) will be compared between the BPTx and the control groups. A table of comparative

studies using the Peritron device to measure PFM strength changes with PFM therapy is provided in Table 12 below.

Based on the existing comparative studies using the Peritron, continent women have a maximum amplitude PFM contraction between 36-45 cm H₂O. Incontinent women have significantly lower maximum contractions, ranging from 15.5 to 26.5 cm H₂O, with most studies showing a maximum contraction of 25 cm H₂O. In these studies, incontinent women can improve their maximum contraction pressure up to 34-41 cm H₂O with PFM training, which is comparable to continent women. In addition, these studies report women experience significant improvement in UI symptoms, although there is limited information on the direct specific relationship between PFM strength changes and UI symptom changes.

Assuming that women in ESTEEM will have a mean baseline PFM maximum contraction amplitude of 25 cm H₂O, and that women randomized to control will not demonstrate significant improvement postoperatively (no change from mean maximum amplitude of 25 cm H₂O (SD 13), and that women randomized to BPTx will demonstrate improvement to 35 (SD 13) to 40 (SD 16) cm H₂O at 6-12 months, the power to detect a difference between the groups with the current ESTEEM sample size of 400 women would be greater than 0.99. Also, the difference from 25 (SD 13) that we could detect with 80% power is 3.66 cm H₂O between groups and with 90% power we could detect a difference as small as 4.23 cm H₂O.

For analyses, we will compare the mean change from baseline in PFM maximum contraction strength between the BPTx and control groups at 8 weeks and at 12 months. General linear mixed modeling will be used, controlling for stratification factors and time (8 weeks and 12 months). We will test whether there is significant interaction between treatment group and time. Because additional treatment is not expected to impact this outcome, it will be ignored for the purpose of this analysis. We will estimate the correlation between PFM strength and UI symptoms at baseline and at 12 months. Using regression models, we will also explore potential predictors of unsuccessful pelvic floor muscle strengthening and urge suppression and their effects on urinary outcomes. We will assess the effect of self-efficacy^{114, 115}, adherence, and barriers to performing pelvic muscle contractions and behavioral therapy.

Table 12. Comparative studies using Peritron measurement of pelvic floor muscle strength

Author	Pop	Study details	Baseline PFM strength (SD)*	Post-treatment PFM strength (SD)	P-value	Notes
Rett 2007 ¹¹⁶	SUI	N=26 Single cohort PFME with sEMG biofeedback	Max amp= 24.5 (16)	After 12 sessions: 40.0 (17)	<.0001	No info on "subjective improvement" and PFM strength Overall cohort: Obj cure = 61.5% Subj cure = 23% Subj "almost cure"=65.4%
Gameiro 2010 ¹¹⁷	Any UI	N=103 RCT G1 =vag cones G2 =APFMT	Max amp: G1=24.4 (12.5) G2=20.0 (12.9)	6 mos: G1=40.8 (15.73) G2=35.16 (11.05) 12 mos: G1=34.98 (13.2) G2=34.12 (9.84)	P<.05 for both	*No specific correlation btwn subjective "cure" and PFM strength; however: a. Reduction of pads better for G1 b. # micturitions, nocturia, UI episodes, urgency, pad test ND btwn grps
Amaro 2005 ¹¹⁸	SUI	N=101 Comparative cohort G1 = SUI	Max amp: G1=26.1 (1.15) G2=38.4 (1.33)		P<.001 for all 3 baseline	

		G2=controls	Mean amp: G1=15.4 (.62) G2=28.1 (1.22) Duration (s) G1=8.9 (.17) G2=11.8 (.96)		comparisons	
Gilling 2009 ¹¹⁹	SUI	N=70 RCT G1=Estim G2=Sham	Max amp: G1=17.3 (1.8) G2=15.5 (1.9)	8 wks: G1=19.2 (2) G2=15.1 (1.9)	ND	Subgroup findings: "Patients with poor initial PFM ctx by perinometer randomized to Estim had better UI outcomes than sham" but cannot tease out their PFM scores
Hung 2011 ¹²⁰	Any UI	N=23 PMT Prospective cohort, pre- post- PFM program 65% SUI 35% MUI 39% UUI	Max amp: 27 (15.0)	4 mos: 41 (24.9)	<.001	
Gamerio ¹²¹	SUI vs UUI	N=51 Cross-sectional G1=SUI (N=22) G2=UUI (N=29)	Max amp: G1=26.5 (3) G2=21.7 (.79) Mean peak G1=16.56 (1.19) G2=13.72 (0.56) Duration: G1=9.54 (0.18) G2=8.43 (.42)		P<.001 for all 3 baseline comparisons	Unclear clinical meaning

h. To determine the cost effectiveness of combined midurethral sling (MUS) and peri-operative behavioral/pelvic floor therapy (BPTx) compared to MUS alone on successful treatment of MUI symptoms

Differential mean costs and differential mean QALYs between the two treatment groups will be estimated using multiple regression analysis. Specifically, a generalized linear model with appropriate link function (e.g., log-link) and response probability distribution (e.g., gamma distribution) will be used to analyze costs due to the potential skewness and heteroscedasticity of medical expenditure data, while an ordinary least squares regression will be used for analyzing QALY data. The models will account for treatment group, study site and stratification factors, as well as other characteristics of the subjects that are found to differ significantly between the groups. When estimating QALYs, we will also adjust for subjects' baseline utility scores to account for potential imbalance in baseline utility between the two treatment groups.¹²²

We will calculate the incremental cost-effectiveness ratio (ICER), which is the differential mean costs divided by the differential mean QALYs between the two groups, to assess the additional costs associated with each additional QALY gained. Our base case analysis will be conducted based on subjects with complete data. Sensitivity analysis will be conducted to include subjects with incomplete data using the multiple imputation method. Non-parametric bootstrapping resampling technique will be used to derive the 95% confidence interval for the ICER.^{118, 123} In addition, cost-effectiveness acceptability curve (CEAC) will be generated to illustrate the likelihood that one treatment is more cost-effective than the other with various ceiling cost-effectiveness ratios.

In the case that a statistically significant difference in changes in utilities (as measured by EQ-5D) between the treatment groups is not detected, we plan to conduct supplemental analyses using alternative

outcome measures, such as incremental cost per treatment success, incremental cost per HRQOL, or incremental cost per satisfaction.

The cost-effectiveness evaluations will be conducted as within-trial comparisons. A decision analytic model will also be developed from trial data to evaluate the trajectory of the cost-effectiveness ratio over a lifetime; assuming an average life expectancy, given the average age of participants at the time of the intervention.

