3.3. Randomization and Stratification

Patients will be assigned to one of the two treatment groups with a randomization sequence prepared and maintained centrally by the Data Coordinating Center (DCC). Allocation to the treatment groups will be 1:1. Randomly ordered permuted blocks will be used, with block sizes known only by the DCC. The web-based data management system will provide the treatment assignment for each participant as she is randomized. Thus, the allocation sequence will be concealed from clinical site staff.

Randomization will be stratified by clinical site. It is important that UUI “severity” is comparable in both groups as it is a potential risk factor for treatment failure. Therefore, randomization will also be stratified based on UUI “severity” which will be defined by the number of urgency urinary incontinence episodes (IEs) on diary. This will ensure that women who have more frequent, or more “severe” UUI are equally distributed between the two groups. SUI severity is less of an issue because all subjects will be receiving the same treatment for SUI.

[figure not shown]
Burgio et al,⁴³ identified risk factors for unsuccessful behavioral treatment of urge/urge-predominant MUI. Women who had ≥ 10 IE/week on a 7-day diary at baseline were much less likely to be completely continent after behavioral treatment. Therefore, for a 3-day diary, this would translate into ~ 4 IEs on a 3-day diary as a potential risk factor for treatment failure.

There is limited data to support stratification based on presence of preoperative DO on UDE. One study found that up to 38% will have resolution of DO after MUS.⁴⁴ Other studies suggest that baseline DO is a risk factor for postoperative UUI.⁴⁵ Still other studies even suggest that baseline DO is associated with greater improvement in OAB symptoms postoperatively. Choe et al evaluated 132 women with MUI who underwent MUS and found a higher proportion of women with preoperative DO had complete resolution of OAB symptoms postoperatively compared to those without DO (37% vs. 18%).⁴⁶ A secondary analysis of TOMUS data supported that more severe UUI (by MESA score) was a risk factor for non-SUI sling failure after MUS (or failure due to UUI);²⁹ however, baseline DO was not a risk factor (28% vs 21% objective failure for women with and without DO, respectively).³⁰

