We plan to capture incremental direct health care, direct non-medical, and indirect resource use related to study interventions and complications and other urinary incontinence management (such as other UI treatment, UI products and management of side effects). Costs will be estimated using the resource costing method. Direct medical service use collected from each study case report form and direct non-medical and indirect costs collected from patient questionnaires are monetized by multiplying the number of units of each resource use by the average unit cost of this item in dollars. Detailed individual cost data will not be collected. This method allows a consistent capture of resource use when costs are incurred across multiple health systems or payers. Detailed case report forms, that include the interventions performed (e.g. midurethral sling surgery and behavioral/pelvic floor therapy sessions) and clinical events (e.g. complications and additional treatment) will be completed by the study coordinator at study visits. Patient questionnaire on direct non-medical costs (e.g. pads, laundry) and indirect costs (e.g. time, lost productivity) will be completed at study visits 3, 6 and 12 months. Data from medical resource types (physician visits, behavioral/pelvic floor therapy sessions, medications, hospital admissions and emergency room visits) will be collected. Cost for each direct medical service use, direct non-medical items, and indirect items will be assigned based on national Medicare reimbursement rates or other standardized unit costs as indicated in the following Table 5.

Table 5: Resource utilization data collection and price data source, by utilization category

Service	Source Documentation	Price Weight
Surgery: midurethral sling	Case Report Form	Medicare reimbursement
Behavioral/pelvic floor therapy	Case Report Form	Medicare reimbursement
Medication	Case Report Form	Drug Red Book
Physician visit	Case Report Form	Medicare reimbursement
Complication: surgery	Case Report Form	Medicare reimbursement
Complication: hospitalization	Case Report Form	Medicare reimbursement
Complication: ER visit	Case Report Form	Medicare reimbursement
UI products	Questionnaire	Average national cost
UI laundry / dry cleaning	Questionnaire	Average cost
Time	Questionnaire	Average cost
Lost Productivity	Questionnaire	Average cost

Rationale for using the EQ-5D to measure Utility Values

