The European Quality of Life-5 Dimensions (EQ-5D) (EuroQol Group, <http://www.euroqol.org>), preference-based utility index algorithm will be used to calculate each subject’s utility index.⁶⁹ This instrument will be collected at baseline and follow up study visits (3, 6, and 12 months). The EQ-5D has 5 attributes (mobility, self-care, usual activities, pain/discomfort and anxiety/depression) with 3 levels each for a possible 243 unique health states. The EQ-5D scoring Function is based on the time-tradeoff method with UK Scores ranging from -0.59 to 1.00 and US Scores from -0.11 to 1.00. This instrument has been previously validated in women with urinary incontinence (Penn preliminary data, Tables 6 and 7) and used in women with urinary incontinence.^{70, 71} These data will be used to compare change in QALYs between the two treatment groups. We are choosing to use a general scale to calculate change in utilities (rather than condition-specific) to allow for comparison of cost-effectiveness results with other interventions and diseases.

A questionnaire to measure direct non-medical costs (e.g. pads, laundry) and indirect costs (e.g. time, lost productivity) will be administered. Based on similar questionnaires used in SISTEr¹⁷ and ValUE⁷² studies, this instrument should take approximately 15 minutes for a subject to complete at baseline and 3, 6 and 12 months.

Table 6: Mean utility preference scores for women with urge incontinence, stress incontinence and mixed incontinence.

	UUI (n = 40)	MUI (108)	SUI (n=54)	p-value ^a
HUI-3	0.78 ± 0.23	0.79 ± 0.24	0.86 ± 0.15	0.29
EQ-5D	0.71 ± 0.23	0.73 ± 0.26	0.81 ± 0.16	0.02
SF-6D	0.76 ± 0.12	0.74 ± 0.12	0.81 ± 0.11	0.02
VAS ^b	0.78 ± 0.15	0.78 ± 0.16	0.80 ± 0.14	0.63

UUI = urge incontinence SUI = stress incontinence, MUI = mixed urge and stress incontinence

^a Kruskal Wallis ^b VAS scores were divided by 100 to enhance comparability

Table 7: Utility preference score correlations with symptom severity and condition-specific HRQOL measures

	HUI-3	EQ-5D	SF-6D	VAS
	r-value ^a	r-value ^a	r-value ^a	r-value ^a
PFDI-20 score	-0.32	-0.42	-0.37	-0.22
Bladder subscore	-0.16	-0.26	-0.24	-0.23
PFIQ-7 score	-0.45	-0.48	-0.50	-0.32
Bladder subscore	-0.29	-0.31	-0.41	-0.26

Lower scores on the HUI-3, EQ-5D, SF-6D and VAS represent worse utility values while higher scores on the PFDI, ISI and PFIQ represent worse symptom severity and quality of life. ^a Spearman correlation

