i. Primary outcome: MUI symptoms = UDI-total score

The MID for the UDI-total score published by Dyer et al is estimated to be 35 points.⁵⁰ Assuming a two-sided alpha of .05, SD of 50.4, and true difference in mean change from baseline in UDI-total scores at 1 year between treatment groups of 35, 75 women per group would provide 90% power to detect a statistically significant difference between groups.

ii. Secondary outcome: OAB symptoms= UDI-irritative subscale: For the UDI-irritative subscale, the published MID estimate is 15 points.⁵⁰ Assuming a two-sided alpha of 0.05, SD of 25.6, and true difference in mean change from baseline in UDI-irritative scores at 1 year between treatment groups of 15, 92 women per group would provide 90% power.

iii. Secondary outcome: SUI symptoms = UDI-stress subscale: For the UDI-stress subscale, the published MID is 8 points.⁵¹ Assuming a two-sided alpha of 0.05, SD of 21.5, and true difference in mean change from baseline in UDI-stress scores at 1 year between treatment groups of 8, 200 women per group would provide 90% power to detect a statistically significant difference between groups.

Using 200 per group as our base estimate and adjusting for 15% dropout post-operatively results in a total sample size of 472 randomized to treatment.

Additionally, this sample size will provide approximately 90% power to detect a difference as small as 19 between treatment groups for the UDI-total score, and a difference as small as 16.5 points with 80% power.

6.1.2. Potential limitations of the UDI and primary outcome:

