One potential limitation of using change from baseline score as the primary outcome is that point estimates of the difference in means between 2 groups may mask important changes for individual patients that are meaningful. However, this would also be the case if we dichotomized the outcome into “success” versus “failure”. In addition, the published MID used for our primary outcome is derived from the BE-DRI population, an urge-predominant MUI population and MID estimates can vary depending on the study population. The published estimate for UDI-total MID for the BE-DRI urge-predominant population is 35 points based on Dyer et al⁵⁰ whereas Barber et al found the MID for pure stress/stress-predominant population to be 11 points in the ATLAS population.⁵¹ One advantage of the BE-DRI population is that 96% had MUI, which is more similar to the anticipated ESTEEM population. It is possible that women with UUI require larger improvements compared to pure/SUI predominant women to be meaningful. This is consistent with many previous studies showing that women with UUI experience worse impact and bother than SUI patients and that the UUI component drives patient perception of severity and satisfaction after treatment.

Although we do not definitively know whether 35 is an accurate MID for determining success or failure in this study population, we consider this MID estimate from BE-DRI to be the published MID that is most applicable to our target population. In addition, because our total sample size is 400 subjects (before adjustment for drop out), our study will have 90% power to detect a statistically significant difference in UDI-total scores if the true difference is as small as 19 points between groups and 80% power to detect a difference if the true difference is as small as 16.5 points. This difference is smaller than the conservative, distribution-based MID estimate of -24.8 based on the BE-DRI population. Thus, the planned sample size will allow for analyses to assess whether the true MID in this population is smaller than 35.

Finally, the UDI total score includes 3 subscales: stress, irritative and obstructive. Therefore, our primary outcome will include a total score combining all 3 of these subscales. We believe the inclusion of the obstructive subscale is appropriate for the following reasons:

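### The headline cost-effectiveness result rests on women with complete data, while multiple imputation, which could use their partial follow-up, is only a sensitivity analysis

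*Protocol*

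**What the plan says.** Protocol 6.2.3 item h sets the main population for the incremental cost-effectiveness ratio: "Our base case analysis will be conducted based on subjects with complete data". Women with gaps come in afterwards: "Sensitivity analysis will be conducted to include subjects with incomplete data using the multiple imputation method". The interval for the ICER is to come from a non-parametric bootstrap, and an acceptability curve (CEAC) is also planned.

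Protocol 3.4.3.f describes the data. EQ-5D is scheduled at baseline and at 3, 6 and 12 months. The patient questionnaire on non-medical and indirect costs "will be completed at study visits 3, 6 and 12 months"; a later paragraph of the same section adds baseline. Table 5 takes the other cost categories from case report forms.

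Item h models costs with a generalised linear model and QALYs with least squares. Both adjust for arm, site, stratification factors and characteristics that differ between arms; the QALY model also adjusts for baseline utility. Interim utilities and costs are not covariates.

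The SAP does not change this. It lists cost-effectiveness as exploratory aim 8 (3.1.3) but has no section on its analysis. SAP 7.3 plans no imputation for secondary analyses, and Attachment 16.2 covers only UDI total and the dryness and MID indicators.

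**The concern.** A QALY over 12 months is built from utilities at successive visits, so on the natural reading of complete data a woman with a gap at one visit drops out of the base case and her observed visits go unused. The UDI analysis treats the same woman differently. SAP 5.1 includes anyone with outcome data at any follow-up from 3 to 12 months, and SAP 9.1 relies on missing at random, with the 3- and 6-month scores informing a missing 12-month score. A woman seen at 3 and 6 months and then lost would count in the UDI result but not in the headline ICER.

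Two things are at stake. One is precision. The other is the assumption: the complete-case regressions need completeness to depend on nothing related to outcome beyond the baseline variables in the model, whereas imputation can also condition on the utilities, costs and symptoms already observed during follow-up. The lifetime decision model in item h is also to be developed from trial data, so it may inherit any selection.

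**Working it through.** **Step 1: reproduce the plan's own figure.** Inputs from Protocol 6.1.1: "Using 200 per group as our base estimate and adjusting for 15% dropout post-operatively results in a total sample size of 472".

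- 200 / (1 − 0.15) = 235.3, rounded up to 236 per group.
- 236 × 2 = 472, which matches.

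This is the only attrition figure in the documents. No completeness rate is given for EQ-5D or cost forms.

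**Step 2: women left out at the planned dropout alone.**

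- 472 − 400 = 72 women, and 72 / 472 = 15.3%. (Applying 15% directly gives 0.15 × 472 = 70.8; the difference is rounding.)

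If the 15% is realised and complete data means all scheduled forms, this is a floor, because retained women can still miss a visit or a form.

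**Step 3: add missed forms among retained women.** Let m be the share of retained women with missing forms at a visit, independent across visits, and k the number of visits at which this can happen. Both m and independence are assumptions.

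Incomplete share = 1 − 0.85 × (1 − m)^k; women left out = 472 × that share.

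| m (assumed) | k = 2 (3 and 6 months) | k = 3 (3, 6 and 12 months) |
|---|---|---|
| 0% | 15% (71) | 15% (71) |
| 3% | 1 − 0.85 × 0.97² = 20% (95) | 1 − 0.85 × 0.97³ = 22% (106) |
| 5% | 1 − 0.85 × 0.95² = 23% (110) | 1 − 0.85 × 0.95³ = 27% (128) |
| 10% | 1 − 0.85 × 0.90² = 31% (147) | 1 − 0.85 × 0.90³ = 38% (180) |

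If the 15% already means lost by 12 months, the three-visit column may count the 12-month visit twice, so the two-visit column is the safer one.

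**Step 4: what a quarter would need.** Solving 0.85 × (1 − m)^k = 0.75 gives m = 1 − (0.75 / 0.85)^(1/k), which is 6.1% for k = 2 and 4.1% for k = 3.

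**Step 5: precision.** With standard errors proportional to 1/√n, the base case against complete data on all 472 gives √(472/400) = 1.09 at the floor and √(472/344) = 1.17 at the 27% scenario (472 − 128 = 344). Imputation would recover only part of this.

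**Step 6: the assumptions side by side.** The complete-case base case allows completeness to depend on arm, site, strata, imbalanced characteristics and, for QALYs only, baseline utility. Missing at random with an imputation model that includes interim data allows it to depend on all of these plus observed 3- and 6-month utilities, costs and UDI. Where the baseline covariates are observed, the first condition is a special case of the second, so it is the stronger one.

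**The case against.** The strongest reply is that this is a choice of label between two analyses that are both specified in advance, for an exploratory aim, and that readers will see both results. That is largely fair, and it limits the weight of the point. It does not remove it, because the label decides which ICER is quoted.

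Several stronger readings are tempting, and the documents do not support them:

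- **That about a quarter of women are lost.** The documents give 15%. A quarter needs the added missed-form rates in Step 4.
- **That these women are discarded.** The sentence after the base case brings them back by imputation.
- **That one missing form always removes a woman.** This is the natural reading, but complete data is not defined, and many cost items come from coordinator-completed forms.
- **That women who do badly are the ones missing, so the ICER is biased in a known direction.** Nothing shows this. Assessments are scheduled for all women, those starting additional treatment are asked to complete outcome measures first (Protocol 3.4.1.c), and coordinators pursued out-of-window visits (SAP 7.9).
- **That the rest of the trial uses partial data under missing at random.** This holds for the longitudinal mixed models. The voiding-frequency and dryness indicators are summarised among non-missing values (SAP 9.2), and imputation is a sensitivity tool even for UDI total.

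It also stands that complete-case regression is not invalid in itself. It is valid if completeness depends only on the covariates in the model and the model is correctly specified.

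**Conclusion.** The concern holds as a modest improvement to exploratory aim 8. The base-case ICER would omit women with partial follow-up and would need a stronger missing-data assumption than the UDI mixed model.

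Its size is at least about 72 of 472 women if the planned 15% dropout occurs. It becomes 20-23% with an assumed 3-5% of missed forms at each of two interim visits, or 22-27% if the same rates apply at three. These figures rest on complete data meaning all scheduled forms, and on independence across visits. The size and direction of any bias cannot be determined from the documents. No primary or secondary test is affected.

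**What to change.** In Protocol 6.2.3 item h, and in a short cost-effectiveness section of the SAP:

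1. Make multiple imputation the base case and report complete cases as the sensitivity analysis.
2. Specify the imputation model: run by arm, with baseline and interim utilities and costs, UDI, the stratification factors and additional treatment. The variable list in SAP Attachment 16.2 cannot simply be reused, since it omits utilities, costs and additional treatment.
3. State how imputation and the bootstrap are combined, including their order, for the ICER interval and the CEAC.
4. Define complete data, so that the sensitivity analysis is reproducible, and report the number of women contributing to each analysis by arm.

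The cost is a short specification and somewhat more computing; no new data are needed. Imputation still assumes missing at random and does not protect against missingness that depends on unobserved costs or utilities. Settling the order before the cost-effectiveness results are examined also removes any scope to choose between two ICERs afterwards.
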